3.1.10 At least 1 measurable lesion per RECIST version 1.1

3.1.11 Female patients who:

- Are postmenopausal for at least 1 year before the screening visit, OR
- Are surgically sterile, OR
- If they are of childbearing potential, agree to practice 2 effective methods of contraception, at the same time, from the time of signing the informed consent through *4 months* after the last dose of study drug, or agree to completely abstain from heterosexual intercourse. (Oral and implantable contraceptives are not considered effective forms of contraception for study purposes. See Appendix C (auxiliary patient document)).
- Women of child-bearing potential (WOCBP) must have a negative serum pregnancy test within 7 days of D1 of treatment.
- 3.1.12 Male patients, even if surgically sterilized (i.e., status post-vasectomy), who:
 - Agree to practice effective barrier contraception during the entire study treatment period and through 4 *months* after the last dose of study drug, or
 - Agree to completely abstain from heterosexual intercourse
- **3.1.13** Ability to provide signed informed consent and willing and able to comply with all study requirements.

3.2 Inclusion criteria for cohort assignment

- **3.2.1** Cohort A: Progressive disease on any next generation ALK inhibitor except first line alectinib alone (eligible for study but assigned to cohort B) or brigatinib (any line). Patients who received previous therapy with lorlatinib will be assigned to cohort A.
- **3.2.2** Cohort B: Progressive disease on first-line therapy with alectinib, and no other ALK inhibitors
- **3.2.3** Cohort C: Previous treatment brigatinib at 180 mg daily for \geq 4 weeks without > grade 2 drug-related toxicities and with radiographic evidence of

progressive disease and no intervening systemic therapies such as chemotherapy, immunotherapy or another ALK inhibitor (radiation therapy allowed as intervening therapy).

3.2.4 Patients who are treated on cohorts A and B will be allowed to enroll in cohort C if they meet the inclusion and exclusion criteria. Patients are required to undergo a biopsy before enrollment in cohort C. Patients who change cohorts from A or B to cohort C should not have EOT assessments completed and do not discontinue brigatinib, and should complete a new registration form and will be given a new subject number

3.3 Exclusion Criteria for cohorts A, B, and C

[figure not shown]
Patients meeting any of the following exclusion criteria will not be able to participate in this study:

- **3.3.1** History or the presence of pulmonary interstitial disease, drug-related or immune-related pneumonitis, or radiation pneumonitis requiring medical management within 6 months of trial enrollment
- **3.3.2** Prior treatment with brigatinib for cohorts A and B
- **3.3.3** History of or active significant gastrointestinal (GI) bleeding within 3 months
- **3.3.4** Malabsorption syndrome or other GI illness that could affect oral absorption of the study drug
- **3.3.5** Received cytotoxic chemotherapy, investigational agents or radiation within 7 days prior to D1 of study treatment
- **3.3.6** Received prior ALK TKI therapy within 7 days prior to D1 of treatment under study drug. 7 day wash out period is required after prior ALK inhibitor treatment for cohorts A and B. Patients enrolling in cohort C should continue brigatinib and 7 day wash out is not required).
- **3.3.7** Have significant, uncontrolled, or active cardiovascular disease, specifically including, but not restricted to:
 - Myocardial infarction (MI) within 6 months of trial enrollment
 - Unstable angina within 6 months of trial enrollment
 - Congestive heart failure (CHF) with 6 months prior to trial enrollment
 - Any history of ventricular arrhythmia
 - Cerebrovascular accident or transient ischemic attack within 6 months of D1 of study treatment
 - Clinically significant atrial arrhythmia (as determined by the investigator) or severe baseline bradycardia defined as resting heart rate < 60 beat per minute
 - Uncontrolled hypertension defined as baseline SBP> 160 and DBP > 100 on 3 separate clinic visits or past history of hypertensive urgency, emergency, or encephalopathy

[figure not shown]
- **3.3.8** Another primary malignancy for which the patient is currently receiving therapy
- **3.3.9** Have been diagnosed with another primary malignancy within the past 3 years (except for adequately treated non-melanoma skin cancer, cervical cancer in situ, or prostate cancer, which are allowed within 3 years)
- **3.3.10** Have symptomatic CNS metastases which require an increasing dose of corticosteroids within the last 2 weeks to remain asymptomatic.
- 3.3.11 Have active infection requiring intravenous antibiotics
- **3.3.12** Pregnant or breastfeeding
- **3.3.13** Have any condition or illness that, in the opinion of the investigator, would compromise patient safety or interfere with evaluation of the study drug.

4.0 TREATMENT PLAN

4.1 Schema for cohorts A and B

4.2 Schema for cohort C

4.3 Treatment Dosage and Administration

4.3.1 Cohorts A and B

Brigatinib will be administered at a dose of 90 mg (3 by 30 mg tablets) orally once a day (QD) for the first 7 days of cycle 1 followed by 180 mg (6 by 30 mg tablets) orally once a day continuously thereafter. NOTE: during cycle 1, patients will be seen on D8 to determine if dose escalation to 180mg is appropriate (see section 4.3.1 and 4.3.2. Should drug formulation change, equivalent doses in smaller numbers of capsules may be substituted to reduce patient pill burden in any cohort.

A cycle of therapy will comprise 28 days of treatment, regardless of dose. Patients will be instructed to take the prescribed dose with water (recommended 240 mL(8 oz)) at the same time each day, and *without regard to food intake*. Patients who forget to take their scheduled dose of study drug should be instructed not to make up the missed dose. Patients who vomit immediately after taking a dose should be instructed NOT to retake the dose. All doses should be recorded in the patient diary, with a notation made by the patient if any dose is missed, or if a dose is vomited.

4.3.2 Cohort C

Brigatinib will be administered at 240 mg daily (8 by 30 mg tablets). A cycle of therapy will comprise 28 days of treatment, regardless of dose. Patients will be instructed to take the prescribed dose with water [recommended 240 mL (8 oz)] at the same time each day, and without regard to food intake. Patients who forget to take their scheduled dose of study drug should be instructed not to make up the missed dose. Patients who vomit immediately after taking a dose should be instructed NOT to retake the dose. All doses should be recorded in the patient diary, with a notation made by the patient if any dose is missed, or if a dose is vomited.

4.4.2 Hematologic Treatment-Related AEs during Brigatinib 90mg Daily 7 day lead-in

Grade ¹	Dose Modification	Criteria for Dose Escalation
1 or 2	Continue 90mg daily	Escalate to 180 mg daily D8 as scheduled
3 or 4	Hold until event is \leq Grade 2 or returned to baseline, then resume 90mg daily	Do NOT escalate dose
¹ Per NCI CTCAE v4.0		

4.4.3 Non-Hematologic Treatment-Related AEs during Brigatinib 180mg Daily other than Pneumonitis

Grade ¹		Dose Modification
1 or 2	Continue current dose	

3	• When the current dose is 180 mg QD: Hold until event is grade ≤ 1, or has returned to baseline. Resume at 180 mg QD or 120 mg QD at the discretion of the investigator
	• Upon recurrence at 180 mg QD: Hold until event is grade ≤ 1, or has returned to baseline and resume at 120 mg QD
	• When the current dose is 120 mg QD: Hold until event is ≤Grade 1, or has returned to baseline. Resume at 90 mg QD after recovery
	• When the current dose is 90 mg QD: Hold until event is ≤Grade 1, or has returned to baseline. Resume at 60 mg QD after recovery, or discontinue at the discretion of the Investigator.
	• When the current dose is 60 mg QD: Consider discontinuing treatment at the discretion of investigator
4	• When the current dose is 180 mg QD: Hold until event is grade ≤1, or has returned to baseline. Resume at 120 mg QD, or discontinue, at the discretion of the investigator
	 When the current dose is 120 mg QD, hold until event is grade ≤ 2, or has returned to baseline. Resume at 90 mg QD after recovery
	• When the current dose is 90 mg QD: Hold until event is grade ≤ 1, or has returned to baseline. Resume at 60 mg QD after recovery, or discontinue at the discretion of the Investigator
	• When the current dose is 60 mg QD: Consider discontinuing treatment at the discretion of investigator
¹ Per NCI CTCAI	E v4.0

4.4.4 Hematologic Treatment-Related AEs during Brigatinib 180mg Daily

Grade ¹	Dose Modification
1 or 2	Continue at same dose

3	• When the current dose is 180 mg QD: hold until event is grade ≤ 2, or has returned to baseline. Resume at 180 mg or 120 mg QD at the discretion of the investigator
	• Upon recurrence at 180 mg QD: Hold until event is grade ≤ 2, or has returned to baseline. Resume at 120 mg QD
	• When the current dose is 120 mg QD: Hold until event is grade ≤ 2, or has returned to baseline. Resume at 90 mg QD
	• When the current dose is 90 mg QD: Hold until event is grade ≤1, or has returned to baseline. Resume at 60 mg QD after recovery, or discontinue at the discretion of the investigator
	• When the current dose is 60 mg QD: Consider discontinuing treatment
4	• When the current dose is 180 mg QD: Hold until event is grade≤ 2, or has returned to baseline. Resume at 120 mg QD after recovery
	• When the current dose is 120 mg QD, hold until event is grade ≤ 2, or has returned to baseline. Resume at 90 mg QD after recovery
	• When the current dose is 90 mg QD: Hold until event is ≤Grade 1, or has returned to baseline. Resume at 60 mg QD after recovery, or discontinue at the discretion of the Investigator
	• When the current dose is 60 mg QD Consider discontinuing treatment
¹ Per NCI CTO	CAE v4.0

4.4.5 Treatment-Related Pneumonitis during Brigatinib 90mg Daily 7 day lead-in

Grade ¹	Recommended Action
1	• Withhold the dose until pneumonitis returns to grade 0 (baseline), then resume at 90 mg and do not escalate.
	• If pneumonitis recurs, permanently discontinue treatment.
2	 Withhold dose until pneumonitis returns to grade 0, then resume at 60 mg and do not escalate. If pneumonitis recurs, permanently discontinue treatment.
3 or 4	Permanently discontinue treatment
¹ Per NCI CT	CAE v4.0

Grade ¹	Recommended Action
1	• Withhold the dose until pneumonitis returns to grade 0 (baseline), then resume at same dose.
	• If pneumonitis recurs, permanently discontinue treatment.
2	 Withhold dose until pneumonitis returns to grade 0, then resume at 120 mg QD. If pneumonitis recurs, permanently discontinue treatment.
3 or 4	Permanently discontinue treatment
¹ Per NCI CT	CAE v4.0

4.4.6 Treatment-Related Pneumonitis during Brigatinib 180mg Daily

4.5 Toxicities and dose modifications for cohort C

Patients on cohort C will have tolerated brigatinib 180 mg daily and experienced disease progression. Patients will receive 240 mg daily. Since the purpose of this cohort is to investigate doses of brigatinib at dose greater than 180 mg daily and patients have experienced disease progression on that dose, dose reduction to 180 mg daily will not be permitted. One cycle is 28 days.

Dose level	Brigatinib dose	Schedule
1	240 mg	Daily

Brigatinib Dose Modification Recommendations for patients with for pneumonitis for cohort C

Toxicity	Recommended Action
Grade per	
CTCAE v4.0	
Grade 1	Withhold the dose until pneumonitis returns to grade 0 (baseline), then
	resume at the same dose.
	If pneumonitis recurs, permanently discontinue treatment.
Grade 2	Withhold the dose until pneumonitis returns to Grade 0. Resume at 240
	mg daily
	If pneumonitis recurs or remains grade ≥ 1 , permanently discontinue
	treatment.
Grade 3	Permanently discontinue treatment.
Grade 4	Permanently discontinue treatment.
Abbreviations: C	CTCAE=Common Terminology Criteria for Adverse Events; QD=once
daily	

Recommended Action* Toxicity Grade per CTCAE v4.0 Hematologic Toxicity Grade 1 or Grade 2 Continue at current dose Grade 3 First grade AE: Hold until event is \leq grade 1, or has returned to baseline If grade 3 AE for < 7 days then resume therapy at 240 mg daily. If second grade 3 hematologic toxicity occurs then discontinue brigatinib If grade 3 AE for \geq 7 days then discontinue study therapy Discontinue study therapy Grade 4 Nonhematologic Toxicity Grade 1 or Grade 2 Manage the toxicity with supportive care while continuing at the same dose First grade AE: Hold until event is \leq grade 1, or has returned to Grade 3 baseline If grade 3 AE for < 7 days then resume therapy at 240 mg daily. If second grade 3 non-hematologic toxicity occurs then discontinue brigatinib If grade 3 AE for \geq 7 days then discontinue study therapy Discontinue study therapy Grade 4 Bradycardia (heart rate less than 60 bpm) Grade 1 Continue at current dose Grade 2 or Grade 3 Withhold until recovery to \leq grade 1 or to heart rate 60 bpm or above Evaluate concomitant medications known to cause bradycardia, as well as antihypertensive medications If contributing concomitant medication is identified and discontinued, or its dose is adjusted, resume at previous dose upon recover to \leq grade 1 or to heart rate 60 bpm or above If no contributing concomitant medication is identified, or if contributing concomitant medications are not discontinued then discontinue study therapy Grade 4 Discontinue treatment if no contributing concomitant medication is identified

Brigatinib Dose Modification Recommendations for TRAEs (Excluding Pneumonitis) for cohort C

Toxicity Grade	Recommended Action*	
per CTCAE v4.0		
* Apply these recomm	nendations after either dose escalation was accomplished, or after	
dose reduction for gra	n for grade 3 or grade 4 toxicity was implemented resulting in no dose	
escalation.		
Abbreviations: bpm=beats/minute; CTCAE=Common Terminology Criteria for Adverse		
Events; QD=once dai	ly	

4.6 Concomitant Medications/Juices/Herbal Supplements

Patients may receive standard supportive care at the discretion of investigator (i.e. anti-emetics, bisphosphonates, narcotics for pain control, etc.).

In vitro studies suggest that brigatinib, at the doses being evaluated clinically, is unlikely to inhibit CYPs 1A2, 2B6, 2C8, 2C9, 2C19, 2D6, and 3A4/5. Thus, drug interactions (DDIs) due to inhibition of CYPs by brigatinib are highly unlikely. However, other medications that inhibit CYPs may cause DDIs because of their impact on brigatinib's metabolism as outlined in section 1.3.9 and management is outlined in section 4.6.3.

4.7 Prohibited Palliative Radiotherapy

Patients who require palliative radiotherapy for symptomatic or asymptomatic metastases will be considered as experiencing disease progression as per Section 4.5 and will be followed up per protocol.

Patients on cohort A or B who receive local ablative therapies such as radiation to sites of oligo-and/or isolated CNS progression should be considered for cohort C.

4.8 **Prohibited Systemic Therapy**

Patients cannot receive systemic therapy (i.e. chemotherapy or targeted therapy) while on protocol therapy.

4.9 Prohibited Medications/Juices/Herbal Supplements

See section 1.3.9 for rationale of why use of concomitant medications that fall into the following categories are prohibited: medications/juices/herbal supplements that are strong or moderate inducers or strong inhibitors of CYP3A4. Please refer to Appendix C (see as auxiliary patient document).

4.10 Duration of Therapy

Patients should continue on protocol therapy until one of the following events:

- Disease progression
- Inter-current illness that prevents further administration of treatment
- Unacceptable adverse event(s)
- Pregnancy
- Patient decides to withdraw from study treatment, **OR**
- General or specific changes in the patient's condition render the patient unacceptable for further treatment in the judgment of the investigator.

4.11 **Duration of Follow Up**

Long-term follow up will occur every 3 months from the last administration of protocol-directed therapy for up to 2 years or until death, whichever occurs first. Subsequent therapy and survival status will be documented. NOTE: follow-up may occur via review of medical records, on-site visits are not required.

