2.5 Secondary Endpoints

- **2.5.1** The treatment-related adverse events will be assessed using the NCICTCAE version 4.0 as assessed by the investigator.
- **2.5.2** Duration of response is measured from the time measurement criteria are first met for CR/PR (whichever is first recorded) until the first date of progression
- **2.5.3** PFS with progression events as per RECIST 1.1 and as assessed by the investigator; PFS is defined from day 1 of treatment until progression of disease (either intracranial or extracranial) or death as a result of any cause
- 2.5.4 Intracranial PFS is defined from day 1 of treatment until intracranial progression of disease or death as a result of any cause; extracranial PFS is defined from day 1 of treatment until extracranial progression of disease or death as a result of any cause. Only patients with brain metastases at baseline will be included in this analysis
- **2.5.5** OS is defined from day 1 of treatment until death as a result of any cause
- **2.5.6** Intracranial ORR as determined by RECIST 1.1 as assessed by the investigator

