6.0 EVALUATIONS AND ASSESSMENTS

6.1 Time and Events Table

Assessment	Screening 1	C1 D1 ^{1,2}	C1 D8 ²	C2 D1 ^{1,2,} 14	C3 D1 ^{1,2}	C4 D1 ^{1,2,} 14	C5 D1 ^{1,2}	C6 D1 ^{1,2}	C7 D1 ^{1,2}	C8 D1 ^{1,2,} 14	C9 D1 ^{1,2}	C10 D1 ^{1,2,} 14	C11 D1 ^{1,2}	C12 D1 ^{1,2}	EOT ³	FU ⁴
Informed consent ¹²	Х															
Medical History ⁵	Х														Х	
Prior cancer therapy ¹³	Х															
Physical exam & vital signs ^{5, 14}	Х	Х		Х	Х	Х	Х	Х	Х	Х	Х	Х	Х	Х	Х	
ECOG Performance Status	Х	Х		Х	Х	Х	Х	Х	Х	Х	Х	Х	Х	Х	Х	
CBC with differential ⁶	Х	Х	Х	Х	Х	Х	Х	Х	Х	Х	Х	Х	Х	Х	Х	
Serum Chemistries ⁷	Х	Х	Х	Х	Х	Х	Х	Х	Х	Х	Х	Х	Х	Х	Х	
Testosterone (males)	Х				Х		Х		Х		Х		Х			
ECG	Х															
Serum pregnancy Test ⁸	Х															
CT scan chest/abdomen ²	Х				X ²		X ²		X ²		X ²		X ²			
Brain MRI ²	Х				x ²			x ²			X ²			X ²		
Peripheral blood sample ⁹		X ⁹			X ⁹		X ⁹		X ⁹		X ⁹		X ⁹		X ⁹	
Tumor sample	x ¹⁰														X ¹⁰	
Adverse event 5, 14 assessment		Х	Х	Х	Х	Х	Х	Х	Х	Х	Х	Х	Х	Х	Х	
Patient Diary		Provide ¹¹	Review	Review	Review	Review	Review	Review	Review	Review	Review	Review	Review	Review	Review	
Concomitant Meds	Review	Review	Review	Review	Review	Review	Review	Review	Review	Review	Review	Review	Review	Review	Review	
Subsequent Therapy and Survival Status																Х
Brigatinib		See section 4.2 for brigatinib schedule and dose														

Key to Footnotes

¹ Within 28 days prior to Day 1 of brigatinib unless otherwise noted. If screening (baseline) hematology and serum chemistries were performed within 7 days of D1 of cycle 1, these do not need to be repeated.

 2 Unless otherwise noted, a window of 2 days will be applied to all study visits; for every other cycle tumor imaging starting with D1 of cycle 3, imaging may take place within 7 days prior to the study visit to accommodate holiday, weekends, and transportation issues. CT scan should be of the chest and abdomen. The pelvis should only be performed if there is evidence on metastatic disease in the pelvis.

Brain imaging MRI of the brain should be performed at baseline. In patients with known brain metastases MRI is performed every 3 cycles to assess for intracranial disease progression. Patients without brain metastases on screening MRI will undergo repeat brain imaging as clinically indicated or institutional standard (i.e. a specific interval is not mandated by the protocol). If patient cannot tolerate or has contraindication to brain MRI, a CT scan with and without contrast can be used.

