6.3 Treatment Assessments

6.3.1 D1 each Cycle

Tests and procedures in this Section 6.3.1 are to be conducted during each Day 1 cycle visit. Sections 6.3.3 and 6.3.4 include additional assessments to be conducted during each Day 1 at specific numbered cycle visit (e.g., odd cycles, each third cycle visit).

Clinical evaluation: focused medical history on symptoms/adverse events, comprehensive physical examination (to include weight), vital signs, ECOG performance status

Laboratory studies:

- Hematology: CBC with differential
- Serum Chemistries: blood urea nitrogen (BUN), creatinine, bilirubin, ALT (SGPT), AST (SGOT), alkaline phosphatase, amylase, creatinine phosphokinase (CPK).
- Blood sample: A blood sample for ctDNA will be requested (mandatory); see section 6.6 and the laboratory study for additional details. (Cycle 1 Day 1 & Day 1 of every odd cycle- 3, 5, etc.).

Patient diary: Collect, review with patient, and provide patient with new diary. (C1D1- provide patient with initial diary)

Concomitant medications: Review any additions or deletions.

AE: Adverse events will be assessed according to the NCI CTCAE v. 4.0.

6.3.2 D8 Cycle 1

Clinical evaluation: focused medical history on symptoms/adverse events,

Laboratory studies:

- Hematology: CBC with differential
- Serum Chemistries: blood urea nitrogen (BUN), creatinine, bilirubin, ALT (SGPT), AST (SGOT), alkaline phosphatase, amylase, creatinine phosphokinase (CPK)

Patient diary: Review

Concomitant medications: Review any additions or deletions.

AE: Adverse events will be assessed according to the NCI CTCAE v. 4.0.

6.3.3 D1 Cycle 3 and every odd numbered cycle thereafter (Cycle 3, 5, 7, etc.)

Tumor measurement: Tumor imaging should remain consistent throughout study, and should include CT scans of chest and abdomen. Pelvis should only be done if there is known metastatic disease in the pelvis.

Laboratory studies:

• Serum Testosterone: Male patients only

Blood sample: A blood sample for ctDNA will be requested (mandatory); see section 6.6 and the laboratory study for additional details.

6.3.4 D1 Cycle 3 and every third cycle thereafter (Cycle 3, 6, 9, etc.)

Brain metastases: Brain MRI or CT scan with or without contrast should be done every 3 cycles (3 months) for patients with known brain metastases to evaluated for CNS disease progression.

6.3.5 D1 Cycle 2 and each non-imaging even numbered cycle thereafter (Cycle 2, 4 or 8, etc.)

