6.4 EOT Visit

This visit should occur 30 days (+/- 3 days) after brigatinib treatment stops for whatever reason (adverse event, progression, or at discretion of the investigator). Patients who have an ongoing grade 4 AE or SAE at the time of discontinuation from treatment will be contacted every 2 weeks until the event is resolved, determined to be irreversible by the investigator, or until the patient begins an alternate form of treatment.

NOTE: The first EOT follow up visit is to be performed 30 days (+/- 3 days) after the date a participant receives the last dose of study drug. The date of the EOT visit will not match the date the last dose of study drug was administered and should be entered accordingly on the eCRF/EDC system.

Clinical evaluation: focused medical history on symptoms/adverse events, comprehensive physical examination (to include weight), vital signs, ECOG performance status.

Laboratory studies:

- **Hematology**: CBC with differential
- Serum Chemistries: blood urea nitrogen (BUN), creatinine, bilirubin, ALT (SGPT), AST (SGOT), alkaline phosphatase, amylase, creatinine phosphokinase (CPK)

AE: Adverse events will be assessed according to the NCI CTCAE v. 4.0. All SAEs (see section 7.0) ongoing 30 days or more after last dose of study drug is administered should be followed at least every 4 weeks until they resolve to baseline (or CTCAE grade ≤ 1), stabilize, or are considered to be chronic/irreversible regardless of causality. See also section 7 for documentation of AEs/SARs, when applicable, for patients remaining in the study after transition from cohort A or B to cohort C.

Concomitant medications: Review for any changes since previous visit.

Tissue acquisition: At time of progression on study therapy, biopsy will be repeated in patients who consent to this optional biopsy; see section 6.6 and laboratory manual for additional details.

Blood sample: A blood sample for ctDNA will be requested at time of progression on current therapy. Time of progression for cohort C means patient's further progression (as indicated by CT scan) from their entry into cohort C); see section 6.6 and the laboratory study for additional details.

Cohort C: For patients enrolling in cohort C from cohorts A or B end of treatment is not required; however:

- The EOT section of the eCRF form must still be completed;

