- To avoid repeating assessments, EOT (cohort A or B) and screening (cohort C) assessments (including CT scans, brain MRIs, etc.), reasonable efforts should be taken to perform these assessments as standard of care at EOT to be used for cohort C screening assessments;
- Data relevant to each cohort's participation in the study will be independent according to their cohort assignment and recorded on each applicable eCRF for (i.e., EOT for cohort A or B, screening for cohort C).
- In the event of active AE's which continue past the subjects transition to cohort C, and continuing past the transition date, they are to be recorded under the new Subject number within the Medical History Log, to be updated upon change in AE. severity or status.

6.5 **Post-Treatment/Follow-up Assessments**

Long-term follow up will occur every 3 months from the last administration of protocol-directed therapy for up to 2 years or until death, whichever occurs first. Subsequent therapy and survival status will be documented.

Each cohort A, cohort B and cohort C participant's follow-up data will be captured from their time of enrollment in the cohort (for up to 2 years, or until death, whichever occurs first).

NOTE:

- The first post-treatment follow-up is to be performed 30 days (+/- 3 days) after the date a participant receives the last dose of study drug.
- The date of the EOT visit will not match the date the last dose of study drug was administered and should be entered accordingly on the eCRF/EDC system.
- Follow-up may occur via review of medical records, and on-site visits are not required. To maintain the every 3 month follow-up schedule, these methods should be used for long-term follow up of cohort A or B participants, when their participation and treatment in the study continues as a cohort C participant.

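### Tumor status is not collected after brigatinib stops without progression, although PFS, intracranial and extracranial PFS and duration of response depend on it

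*Combined protocol and SAP*

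**What the plan says.** **Follow-up.** Section 4.11: "Long-term follow up will occur every 3 months from the last administration of protocol-directed therapy for up to 2 years or until death". What is collected: "Subsequent therapy and survival status will be documented". The source may be the chart: "follow-up may occur via review of medical records, on-site visits are not required". Section 6.5 repeats this: "Follow-up may occur via review of medical records, and on-site visits are not required".

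**Imaging.** CT is scheduled at "D1 Cycle 3 and every odd numbered cycle thereafter" (6.3.3). For the brain, the table footnote says "In patients with known brain metastases MRI is performed every 3 cycles to assess for intracranial disease progression". In the table (6.1), CT and MRI are marked at screening and at on-treatment cycles. Neither is marked under EOT or FU, and the FU column holds only subsequent therapy and survival status.

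**End-of-treatment visit.** Section 6.4: "This visit should occur 30 days (+/- 3 days) after brigatinib treatment stops for whatever reason". It lists examination, performance status, laboratory tests, adverse events, medications, an optional biopsy and a ctDNA sample, but no tumor imaging. Scans near this visit are mentioned only for patients moving from cohort A or B to cohort C, who have already progressed.

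**Endpoints.** Section 2.5.3: "PFS is defined from day 1 of treatment until progression of disease", or death. Intracranial and extracranial PFS (2.5.4) likewise end at progression in that compartment or at death. Duration of response (2.5.2) ends at progression only; death is not named.

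**Analysis.** Section 8.3 treats patients who cannot have radiographic assessment, for any reason, as non-responders who progress when they discontinue. It also censors patients without an event at last follow-up, and does not tie that date to a tumor assessment.

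**The concern.** Section 4.10 allows treatment to end for unacceptable adverse events, intercurrent illness or withdrawal, and section 4.4 ends it in cohorts A and B after a delay of more than 2 weeks. None of these requires progression. From that day the endpoints still need a progression date, and the schedule has no planned source for one.

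Duration of response is the most exposed. A responder who stops for toxicity has no planned source for the only event that ends the interval, and responders are few. At the target rate of 20% there would be 0.20 × 40 = 8 in a cohort, so one such patient is 1/8 = 12.5% of that analysis. At the minimum of 5 responders it is 1/5 = 20%.

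Cohort C deserves attention because section 4.5 does not permit reduction to 180 mg, so some toxicities that would lead to a lower dose in A and B end treatment there. CNS activity is also part of that cohort's rationale (1.1), so intracranial dates matter.

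**Working it through.** **1. Which rule covers a patient who stops for toxicity after evaluable scans?** The text of 8.3 does not settle it.
- Read literally, the discontinuation rule could make the stop a progression event. But it also labels the patient a non-responder, which cannot fit someone who responded and then stopped.
- The censoring rule uses last follow-up, which after treatment is a survival contact. Until then the patient counts as progression-free although nobody has looked.
- Censoring at the last tumor assessment is the third option, and is not written.

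I use the 2.5.3 definition of PFS. One sentence in 8.3 defines PFS by death alone and needs reconciling with it.

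**2. The plan's own figure.** There is no design figure for PFS or duration of response. The stated 89% power is for response rate. The exact two-stage calculation at a 20% rate (continue with at least 2 of 20, promising with at least 5 of 40) gives 0.069 + 0.045 = 0.114 rejected, hence power 0.886, which agrees. Best overall response is taken from start to end of treatment (6.8.5), so scans after treatment do not enter it.

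**3. How many patients.** The documents' only rates are in the safety summary of the earlier randomized trial (1.3.9): 3.7% (4/109) and 10.9% (12/110) of the two arms stopped for adverse events.
- At 10.9%: 0.109 × 40 = 4.4 patients per cohort; chance of at least one, 1 − 0.891^40 = 0.99.
- At 3.7%: 0.037 × 40 = 1.5 patients.
- Two of the 219 treated patients stopped for neoplasm progression coded as an adverse event, arm not given. If both are among the 12, the rate is 10/110 = 9.1%, or 3.6 of 40.

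**4. What the readings do to median PFS.** Assumptions: exponential times; on-treatment median m = 15.6 months (investigator-assessed, 180 mg arm of the earlier trial); a fraction f stops before progression; after the stop the progression hazard is h times the on-treatment hazard.

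λ = ln 2 / 15.6 = 0.0444 per month. Stop hazard θ = λf/(1 − f) = 0.0444 × 0.109/0.891 = 0.0054. Λ = λ + θ.

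- Stop counted as progression: median = m(1 − f) = 15.6 × 0.891 = 13.9.
- Censored at the stop: Kaplan-Meier estimates λ, so 15.6 whatever h is.
- Progression ascertained: S(t) = e^(−Λt) + θ/(Λ − hλ) × [e^(−hλt) − e^(−Λt)]. For h = 1 this is e^(−λt), median 15.6. For h = 2, S(15.1) = 0.471 + 0.029 = 0.500. For h = 3, S(14.8) = 0.478 + 0.022 = 0.500.
- Only deaths after the stop count, with the patient kept at risk until the survival contact: by simulation (400,000 patients, 24 months of follow-up after the stop, assumed 12-month median survival after progression), about 16.2 for h = 1.

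| Median PFS, months | f = 10.9% | f = 20% (assumed) |
|---|---|---|
| Stop = progression | 13.9 | 12.5 |
| Censored at stop | 15.6 | 15.6 |
| Ascertained, h = 1 | 15.6 | 15.6 |
| Ascertained, h = 2 | 15.1 | 14.7 |
| Ascertained, h = 3 | 14.8 | 14.1 |
| Later deaths only, h = 1 | 16.2 | 16.9 |

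With an assumed 6-month median, f = 10.9% and h = 1, the figures are 5.3 (stop = progression), 6.0 (censored or ascertained) and 6.3 (later deaths only).

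**The case against.** These are descriptive secondary endpoints in separate single-arm cohorts, and ending tumor assessment at discontinuation is a recognized choice. If the hazard does not change after stopping, censoring at the stop is unbiased (15.6 against 15.6). The largest downward shift, to 13.9, comes from the progression-at-discontinuation rule and not from missing data. Sampling error is also larger than any of these shifts: with 40 uncensored patients and a 7-month median, the 95% sampling range is about 4.4 to 10.6 months. All of this stands, and it limits the priority. It does not remove the point. An unchanged hazard after withdrawal of an active drug cannot be checked without the dates, and the plan does not specify censoring at the last scan.

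A reader might infer that these patients have no progression date at all and that PFS cannot be observed for them. The documents do not support that. Section 8.3, read literally, assigns a date at discontinuation. Deaths are followed for up to 2 years and count in PFS and in intracranial and extracranial PFS. On-treatment scans are available, and there is a visit 30 days after the last dose, though without imaging.

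A reader might also infer that any grade 4 event ends treatment in cohort C and that losses there will be large. That table covers treatment-related events, handles pneumonitis separately and makes grade 4 bradycardia conditional. No discontinuation rate for cohort C is given, and its patients must already have had at least 4 weeks at 180 mg without drug-related toxicity above grade 2 (3.2.3).

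**Conclusion.** The point holds in a limited form. Progression after a stop without progression is not ascertained, and 8.3 permits readings that give different answers.

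At 10.9% stopping and an unchanged hazard, the readings span 13.9 to about 16.2 months around a true 15.6. If the hazard is 2 to 3 times higher after the stop, the true median is 15.1 to 14.8, and censoring at the stop still reports 15.6. Duration of response is the most vulnerable, because death is not among its end events and few responders are expected.

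The stopping rate and the 15.6-month median come from a crizotinib-refractory population and are assumptions here. So are the exponential form, the hazard ratios of 1 to 3, the 20% rate and the 12-month survival after progression. The response-rate decision rule and sample size are unaffected. This is an inexpensive improvement worth making, not a flaw that undermines the trial.

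**What to change.** **Collection (4.11, 6.5 and the follow-up eCRF).** For patients who stopped without progression, record from standard-of-care imaging, in the existing 3-monthly chart review:
- date and site (intracranial, extracranial) of first progression;
- date of the last scan without progression;
- start date of any new anticancer therapy.

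**Analysis (8.3).**
- Use these dates for PFS, intracranial and extracranial PFS and duration of response.
- Censor patients without an event at the last tumor assessment, not at last follow-up.
- State how progression after new therapy is handled, so that a later drug's effect is not credited to brigatinib.
- Limit the progression-at-discontinuation rule to a defined group, so that it does not override recorded dates or turn a responder into a non-responder.

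**Cost.** A few fields on a form already completed every 3 months, with no added scan or visit. The drawback is that off-study scan intervals vary, and brain imaging at a fixed interval is not mandated for patients without brain metastases even on treatment. Some dates will be late or missing, and the report should give the scan intervals after the stop.
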